	Amara Drops will be dispensed with 10-20 drops (0.25-0.50ml) taken three times a day prior to meals for 4 weeks. Patients are free to vary the dose between these limits as considered appropriate. The amount taken will be monitored by checking the volume remaining in the bottle at the end of the 4-week intervention. During this time, patients will continue reporting the presence and severity of dyspeptic symptoms and any side effects into the app.
	At the end of the study period (Study Visit #3) the questionnaires including LCT and the ¹³ C-breath test measurement with concurrent high-resolution electro-gastrography (Gastric Alimetry System) and heart rate monitoring plus concurrent assessment of visceral sensitivity will be repeated. Additionally, the patients will be asked if their global satisfaction was better on Amara treatment, whether they wish to continue treatment and /or recommend the treatment to others with similar symptoms. Questionnaires and diary entries on side effects are also available as paper version.
Risk / Benefit Assessment	The initial assessment of patients with functional dyspepsia will adhere to international guidelines on the investigation of this condition. Amara Drops (Weleda) is a proprietary preparation that has been marketed over the counter (OTC) for many years. No serious side effects have been reported. ¹³ C-breath test gastric emptying studies and other measurements of gastric function (e.g. electro-gastrography) are indicated in patients with functional dyspepsia that do not respond to first-line, dietary management, and empirical treatment. These tests are non-invasive and not radioactive and is associated with no adverse outcomes. Clinical validation studies report that the intake of the 400ml (300kcal) Nottingham Test Meal is tolerated by all healthy controls and >95% of patients with functional dyspepsia without inducing vomiting.
Objectives:	The aim of the present study is to find out if the regular intake of Amara has effects on the perceived symptom burden reported by patients with functional dyspepsia. Since dyspeptic symptoms may be associated with abnormal gastric motor and sensory function, these aspects will be assessed by validated methods.

Outcomes:	 Primary objective / outcome measure: change in perceived symptom burden during regular intake of Amara assessed by the Leuven Dyspepsia Score between visit 1 (off treatment) and 3 (on treatment).

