3.5 Dose Rationale

Patients will take 3 x 10-20 drops of Amara before meals daily for four weeks (see section 8.1). The standard dose of this preparation is 10-15 drops before meals to "stimulate the digestive process"; however, patients are encouraged to adapt the dose to their requirements. Patient compliance will be assessed using a smart phone application that will record whether medication was taken and the severity of symptoms at the end of each day. Patient compliance (i.e. actual intake) will be checked by weighing the bottle at the end of the treatment period.

A 2-4-week run-in period between screening and the start of treatment is applied to ensure that the severity of symptoms is representative (patients tend to present during periods with relatively severe symptoms, thus run-in periods reduce the influence of spontaneous "regression to the mean" providing false positive results). The treatment period of 4-weeks is in accordance with the above-mentioned studies for other aromatic bitter substances and represents the minimum recommendation for study duration in functional gastrointestinal disorders.(15)

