4.3 Secondary Objectives

Assess perceived effect of Amara on other gastrointestinal symptoms using validated, patient related outcome measurements (reflux disease questionnaire, IBS Symptom Severity Score).

Assess effect of Amara on (i) visceral sensitivity and (ii) gastric emptying (¹³C-breath test) in patients with functional dyspepsia with validated 400ml Liquid Nottingham Test Meal. Repeat testing will also allow an assessment of reproducibility to be obtained (iii) In a subset of 20 consecutive patients, gastric electrical activity will be measured using the non-invasive Gastric Alimetry System (high-resolution gastric mapping / electro-gastrography) with concurrent heart rate monitoring.

Participants will be asked also to rate their overall satisfaction with Amara and the number that request an additional prescription of Amara for the period after the study will be documented, as an indication of perceived effectiveness.

Additionally, factors that predict the outcome of Amara treatment in functional dyspepsia will be assessed. These factors will include (i) age (ii) sex (iii) severity of dyspeptic symptoms (iv) presence of other gastrointestinal symptoms (v) presence of psychological comorbidity (vi) presence of heightened visceral sensitivity after ingestion of the NTM (vii) abnormal gastric emptying during ¹³C gastric emptying test (viii) compliance with study procedures.

Additionally, the Lüscher Colour Test will be acquired. This non-verbal, non-written test was developed to provide insights into personality and psychological state. This could be of interest in patients with disorders of brain-gut interaction that may not admit to the role of central factors in their illness. Reproducibility of LCT will be documented by repeating the test at Study visit #1 and #2. Correlation with dyspeptic symptoms, psychological or physiological state will be assessed.

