At the end of the study, all participants will return the supply of Amara. The study team will assess compliance by counting the empty bottles and weighing partly used bottles. Patients will be asked whether they wish to continue the medication (yes / no). If the response is positive, then ongoing treatment will be recommended. Amara is classified by Swissmedic as dispensing category D available following discussion with specialist without prescription ("Abgabekategorie D: «Abgabe nach Fachgespräch»).

Overall, approximately 30 minutes will be needed to complete the questionnaires on each occasion. The total time required per patient during the study is a maximum of 8 hours (reading documents, filling in questionnaires, gastric emptying study (twice)).

During the period the participants are enrolled in this study no additional outpatient examinations are planned. If, while someone is participating in the study, acute symptom occur and the need arises for early outpatient assessment or inpatient admission to the clinic, the study would be terminated for this subject as of this date.

Limitations:

- The study will provide a prospective assessment of perceived treatment effectiveness; however, a large non-specific (placebo) effect is likely to be present as in any open-label, single-arm study in patients with functional gastrointestinal disease. This limitation is factored into the power calculation which requires at least a moderate treatment effect for Amara to be considered effective. Note that the secondary analysis that will identify baseline factors (e.g., age, sex, symptom severity, gastric emptying rate) that associate with treatment effect will be relatively less sensitive to this confounding factor.

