8.4 Compliance with study intervention

Compliance will be assessed by a smart phone app (patients will be asked to confirm intake every day). At the end of the study, the bottles will be weighed to determine the actual dose taken during study procedures. Before analysing the data, we will determine the target-actual-difference of the Amara drops taken for each participant. Less than 50 % of prescribed intake is considered as insufficient compliance. In case of insufficient compliance of participants, those data have to be excluded from the per protocol analysis.

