9.3.2 Study visits

On the second visit, patients will complete a combined assessment of gastric motor and sensory function off treatment with the Nottingham Test Meal, with gastric emptying documented by ¹³C-Breath Testing. On completion of the test, the test substance will be provided to the patient with instructions on how and when to take the Amara. An appointment will be made 4-6 weeks after this appointment for the third and final visit. Based on this, the start day for the intervention will also be determined.

During the 4-week intervention, 10-20 drops of Amara will be taken prior to every meal. Patients will document their symptoms every day using a mobile application. Adverse events can also be recorded. Paper forms are available if required. A reminder will be sent to complete this electronic form every day at 21:00.

Shortly before the third study visit participants receive an e-mail with a questionnaire link. All questionnaires will be completed again. If it is noted during the visit that the questionnaires has not been filled in, this can be done in the waiting room or during the visit. The patient will complete a combined assessment of gastric motor and sensory function on Amara treatment with the Nottingham Test Meal, with gastric emptying documented by ¹³C-Breath Testing. On completion of the test, in addition to the PROM, the patient will be asked about their subjective assessment of the intervention, whether ongoing treatment is desired and whether they would recommend the treatment to other patients with functional dyspepsia. Additionally, compliance with study procedures will be assessed (bottle(s) of Amara will be weighed). At the end of the study, patients are reimbursed a lump sum of 50 Swiss francs for expenses (gas, parking fee, train ticket etc.). More can be provided if an invoice supported by receipts is sent to the principal investigator.

In a subset of 20 consecutive patients, gastric electrical activity will be measured before, during and after ingestion of the Nottingham Test Meal on the second and third study visit using the non-invasive Gastric Alimetry System (high-resolution gastric mapping / electro-gastrography). Concurrent heart rate monitoring will provide an assessment of cardiovagal tone / autonomic nervous function.

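### Section 4.3 lists compliance as a predictor of outcome, but compliance is recorded during and after treatment and intake may respond to symptoms, and the item contradicts sections 6.1 and 11.4.

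*Protocol*

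**What the plan says.** Section 4.3 (Secondary Objectives) states that "factors that predict the outcome of Amara treatment in functional dyspepsia will be assessed" and lists eight of them. The last is "viii) compliance with study procedures". Section 4.3 does not say how this item is measured, but other sections do:

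- Section 9.3.2 uses the same phrase for the final visit: "compliance with study procedures will be assessed (bottle(s) of Amara will be weighed".
- Section 3.5: "Patient compliance (i.e. actual intake) will be checked by weighing the bottle at the end of the treatment period".
- Section 8.4 adds a second measure: "Compliance will be assessed by a smart phone app (patients will be asked to confirm intake every day".

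On the dose, the Synopsis (Protocol Summary) says "Patients are free to vary the dose between these limits as considered appropriate", and section 3.5 says "patients are encouraged to adapt the dose to their requirements". Section 8.3 adds that the upper limit holds even if symptoms get worse.

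On the predictor analysis, the limitations in section 6.1 say that it "will identify baseline factors (e.g., age, sex, symptom severity, gastric emptying rate) that associate with treatment effect". The regression covariates in sections 11.4, 11.4.2 and 11.4.3 are all baseline variables. Compliance is not among them.

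**The concern.** A predictor of treatment outcome should be fixed before treatment can act on it. The first seven items in section 4.3 (age, sex, dyspepsia severity, other gastrointestinal symptoms, psychological comorbidity, visceral sensitivity, gastric emptying) can all be recorded before the first dose. Item (viii) cannot, by either of its measures.

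The order in time matters more than usual here because intake is left partly to the patient. Someone who feels no benefit may lose interest and take less, so that higher intake goes with more improvement. Someone else who feels no benefit may move up within the range, so that higher intake goes with less improvement. In both cases the symptom course drives intake. The resulting association could be read as a dose-response for the product, or as its opposite, when neither exists.

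Section 6.1 presents the predictor analysis as relatively less sensitive to the placebo effect that burdens a single-arm study. That argument does not carry over to item (viii), because a placebo response or a natural remission may itself change how much a patient takes. The study is also meant to inform a later randomised trial, and a spurious intake-response relation would be a poor guide to it.

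**Working it through.** **1. Timing and consistency.**

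| Place in the protocol | What it fixes |
|---|---|
| 4.3, items (i) to (vii) | can be recorded before the first dose |
| 4.3, item (viii) | compliance, named as a predictor |
| 3.5, 9.3.2 | bottle weighed at the end of treatment |
| 8.4 | intake confirmed daily in the app during treatment; bottle weighed at the end |
| 6.1, limitations | predictor analysis concerns baseline factors |
| 11.4, 11.4.2, 11.4.3 | covariates at baseline; compliance absent |

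Item (viii) is post-baseline by both measures. It fits neither the description in section 6.1 nor the models in section 11.4.

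**2. What bottle weight can show.** Inputs: 10 to 20 drops are 0.25 to 0.50 ml, taken three times a day for 4 weeks (3.1); one bottle holds 50 ml, at least 100 doses of 20 drops (8.1.3).

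- The protocol's own figure is reproduced: 50 / 0.50 = 100 doses.
- Scheduled intakes: 28 × 3 = 84.
- Every intake at 10 drops: 84 × 0.25 = 21 ml.
- Every intake at 20 drops: 84 × 0.50 = 42 ml.
- Half of the intakes at 20 drops: 42 × 0.50 = 21 ml.

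A fully adherent patient on 10 drops and a patient who missed half of the 20-drop doses return the same bottle weight. If the 20-drop volume is taken as the target, the first patient is at 21 / 42 = 50%, exactly on the section 8.4 threshold but not below it.

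**3. Can the outcome alone produce an association?** This was illustrated by simulation with n = 60, 4,000 runs and no effect of dose on outcome. The following values are assumptions that are not in the protocol: improvement with mean 0.4 and SD 1; a starting dose of 15 drops with a random SD of 3 drops, kept within 10 to 20; perceived improvement building up over four weeks, with noise of 0.5 SD. The dose then reacts each week to perceived improvement.

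| Reaction (drops per SD of perceived improvement) | Mean correlation of volume with improvement | Runs with p<0.05 |
|---|---|---|
| 0 | 0.00 | 4% |
| 1 up or down | about ±0.30 | 67 to 68% |
| 2 up or down | about ±0.51 | 99% |
| 3 up or down | about ±0.63 | 100% |

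The sign is positive if patients take more when they feel better and negative if they take more when they feel worse. With no reaction, the false-positive rate is close to nominal. The table shows that the mechanism can work and that its direction is open. It does not estimate what would happen in this trial.

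**The case against.** The case for leaving this alone has substance, and most of it stands.

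- **The specified models are already clean.** No covariate list in section 11.4, 11.4.2 or 11.4.3 contains compliance. In section 11.4.3 intake only selects the per-protocol set. A reader might infer from section 4.3 that the planned regressions are contaminated, but they are not.
- **No inference is claimed.** Section 11.1 calls the secondary outcomes purely exploratory, section 11.4 reports their p-values without claiming significance, and section 6.1 concedes that the design cannot evaluate efficacy. No dose-response analysis is announced. How often p falls below 0.05 is therefore not a criterion that the protocol applies here.
- **Any figure for the size is assumed.** If intake correlated 0.2, 0.3 or 0.4 with symptom change, a Pearson test with 60 patients would reach p<0.05 in about 34%, 66% or 90% of trials. This is only the power of that test at those correlations, and it is no evidence that they would occur.
- **Patients are not instructed to dose by symptoms.** They are free to vary the dose and encouraged to adapt it. A symptom-driven dose is a fair inference from that wording, and no more than an inference.
- **Bottle weight is not the sole definition of compliance.** The app record also counts. It too is post-baseline, but a record of whether the dose was taken is less tied to the chosen number of drops. Under the threshold in section 8.4, a lower permitted dose alone does not make a patient non-compliant.
- **Section 4.1 does not depend on compliance.** Its aim of learning who benefits most refers to the psychological and physiological measurements.

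These points limit the reach of the concern. They do not remove it: section 4.3, followed as written, would still report a variable open to influence from the outcome as a predictor of that outcome.

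**Conclusion.** The point holds in a limited form. Item (viii) is a post-baseline variable placed in a list of predictors. Intake may respond to the symptom course, so its association with LDQ change could run in either direction without any drug effect. The item also contradicts section 6.1 and the covariate lists in section 11.4. Bottle weight adds an ambiguity, since 21 ml fits two quite different patterns of intake.

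The conclusion rests on one inference, that some patients adapt intake to how they feel. The wording of the Synopsis and section 3.5 supports it, but the protocol gives no data on how strongly they would do so. The size and sign of a spurious correlation are therefore unknown.

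The primary before-after comparison and the specified regressions are unaffected. This is a correction worth making to an exploratory objective. It is not a threat to the trial's main result.

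**What to change.** Delete item (viii) from the predictor list in section 4.3, so that the list agrees with section 6.1 and sections 11.4 to 11.4.3.

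Report intake descriptively instead, as a post-baseline variable with two separate measures: volume used, from the bottle weight, and number of app-confirmed days. Keeping them apart helps to distinguish missed intakes from a lower permitted dose. If either is shown next to LDQ change, add a note that intake may depend on the symptom course and that the association is not evidence of prediction or of dose-response.

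The cost is one line in section 4.3 and a table footnote. One exploratory association is no longer presented as a predictor. Dosing and data collection stay as they are.

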4.4 Safety Objectives

Perceived safety and tolerability will be assessed. For this purpose, participants will be instructed to report possible adverse drug events (ADRs)/ side effects during the treatment period. Participants will be encouraged also to report possible late-onset ADRs that occur after treatment.

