neuromuscular activity using a large array of electrodes over the abdomen. The test can help differentiate if patients have gastric neuromuscular dysfunction, gastric sensory disorder, gastric outlet obstruction or a functional (central) cause of symptoms. Individuals that fulfill the diagnostic criteria for functional dyspepsia with postprandial distress syndrome according to the Rome IV criteria will be recruited. At the first study visit (Study visit #1), Symptom questionnaires and other questionnaires to assess general health and psychiatric well-being will be completed at the time of recruitment. To answer the questions, the study participants are sent a one-time link to the questionnaires. Additionally, a Lüscher Color Test (LCT) will be performed. This non-verbal, non-written test has been developed to assess patient's personality and psychiatric state. This could be of interest in patients with disorders of brain-gut interaction that may not admit to the role of central factors in their illness.

Eligible patients will have no clinically relevant medical co-morbidity or previous gastrointestinal surgery and must have had a normal upper gastrointestinal pan-endoscopy in the previous 3 years. If not known, Helicobacter pylori status will be assessed by ¹³C-stool antigen test (repeat endoscopy not required). The first visit is followed by a 2–4-week run-in period. The presence and severity of dyspeptic symptoms will be reported using an on-line application downloaded on the patient's smart phone (an electronic reminder will be sent at 21:00 every day).

The LCT will be repeated during the second study visit (Study visit #2). At this time, gastric function will be assessed by ¹³C-breath test measurements with concurrent assessment of visceral sensitivity.

Amara Drops will be dispensed with 10-20 drops (0.25-0.50ml) taken three times a day before meals for 4 weeks. The patients are free to vary the dose within these parameters as considered appropriate. The amount taken will be monitored by checking the volume remaining in the bottle at the end of the 4-week intervention. During this time, patients will continue entering their symptoms and any side effects into the app.

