9.3 Procedures at each visit

9.3.1 Screening visit

At the orientation consultation/screening visit the investigator will review the case notes, investigation results (e.g., laboratory tests, gastroscopy) and interview the patient to ensure that inclusion and exclusion criteria are met. In order to comply with the inclusion criteria, pregnancy tests will be performed on all women of childbearing age. At the screening visit, the LDS and HADS questionnaires will be completed at the time of recruitment and used as screening instruments. This data will be collected using an on-line application. After inclusion, further health-related questionnaires will be completed and

the Lüscher Color Test will be performed.

A time is booked 2-4 weeks later for the second study visit. A mobile application will be downloaded onto the personal smart phone device (Symptom Tracker, Gastric Imaging & Analysis GmbH). Paper forms are available if required. During the 2-4 week "run-in" period patients will document their symptoms every day using a mobile application. A reminder will be sent to complete this electronic form every day at 21:00.

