10. SAFETY

10.1 Drug studies

The Sponsor's SOPs provide more detail on safety reporting.

During the entire duration of the study, all unexpected adverse events (UAW) and serious adverse events (SAEs) are collected, investigated, and documented in source documents and case report forms (CRF). Study duration encompassed the time from when the participant signs the informed consent until the last protocol-specific procedure has been completed.

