11.4.5 Safety analysis

The side effects will be analysed with descriptive statistics as percentage of total (%) for categorical variables.

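### Non-serious events are routinely asked about only from the start of treatment, and as side effects of Amara, so the untreated run-in gives no off-drug rate for non-gastrointestinal complaints; the protocol's event definitions and collection windows also disagree

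*Protocol*

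**What the plan says.** Section 4.1 makes tolerability one of the study's aims. Section 3.6 states that there is no comparator.

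**Participant reporting is placed in the treatment weeks.**
- Section 4.4: "participants will be instructed to report possible adverse drug events (ADRs)/ side effects during the treatment period". The next sentence extends this beyond treatment: "Participants will be encouraged also to report possible late-onset ADRs that occur after treatment".
- Section 3.1, on the four weeks of Amara: "During this time, patients will continue entering their symptoms and any side effects into the app".
- Section 6.1 describes patients noting, during treatment, effects they believe Amara has caused.
- Section 9.3.1, on the weeks before treatment: "During the 2-4 week 'run-in' period patients will document their symptoms every day using a mobile application". Event entry is not mentioned.
- Section 9.3.2, on the intervention: "Adverse events can also be recorded".

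**Other sections define events and the window differently.**
- Section 5.4 has participants enter perceived events and side effects with the questionnaire, and gives no window.
- Section 9.2.4.1 says that adverse events will be recorded, also without a window.
- Section 10.1 collects unexpected and serious events over the whole study, defined thus: "Study duration encompassed the time from when the participant signs the informed consent until the last protocol-specific procedure has been completed".
- Section 10.1.1 defines an adverse event irrespective of its relation to the product and provides a five-level causality assessment.
- The study schedule lists only serious adverse events, at all three visits.

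**The analysis** in section 11.4.5 is one sentence: "The side effects will be analysed with descriptive statistics as percentage of total (%) for categorical variables".

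**The concern.** The run-in is the only untreated observation time in this single-arm trial. The protocol relies on it for efficacy: sections 3.5 and 6.1 use it against regression to the mean, and section 11.2 takes it as the off-treatment reference. Safety makes no comparable use of it, although the patients, the app and the 21:00 reminder are already in place.

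The reactions the protocol expects are of a kind that also occurs without a drug. Section 3.7 names skin rash and gastrointestinal symptoms. Section 3.4 reports that most past reactions were skin (11) or gastrointestinal (9). In an open-label study, an everyday rash or headache in the treatment weeks can be put down to Amara. Equally, a patient may fail to attribute a real reaction and so not report it. The reported percentage can err in either direction, and nothing collected in the run-in would show which.

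There is also a practical ambiguity: site staff cannot tell from the text whether a non-serious complaint in the run-in has to be recorded.

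**Working it through.** **1. Which rule covers a non-serious rash in run-in week 2?**
- 4.4, 6.1 and 9.3.2: not covered, because no drug has been taken and entry is described for the treatment weeks.
- 9.3.1: covers daily symptoms only.
- 10.1: the window is open, but the event is not serious. Section 10.1.1 defines unexpectedness for drug reactions against the product information, so the term has no clear meaning before a first dose.
- 10.1.1: no causal link is needed, but the definition is written for people given a product.
- 5.4 and 9.2.4.1: could cover it, since neither states a window.

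The sections do not give one answer.

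**2. What an inert product would show.** The protocol gives no background rate, so this is an illustration. Inputs: 60 completers (section 7.4), 4 treatment weeks, and an assumed background rate r of 0.02 to 0.05 non-serious events per patient-week. The share with at least one event is 1 − exp(−4r):
- r = 0.02: 1 − exp(−0.08) = 7.7%; × 60 = 4.6 patients
- r = 0.03: 1 − exp(−0.12) = 11.3%; × 60 = 6.8 patients
- r = 0.05: 1 − exp(−0.20) = 18.1%; × 60 = 10.9 patients

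These figures assume that every complaint is reported. If only half were attributed to Amara and entered, r is halved: 1 − exp(−0.04) = 3.9% to 1 − exp(−0.10) = 9.5%, or 2.4 to 5.7 patients.

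At a higher assumed background of 20% over four weeks and no drug effect, 12 of 60 patients would report an event (exact 95% CI 10.8% to 32.3%). Without a reference, that result looks the same as a 20% reaction rate.

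**3. What the run-in could add.** It offers 60 × 2 = 120 to 60 × 4 = 240 untreated patient-weeks, against 60 × 4 = 240 treated. With Poisson counts at 0.03 per week in both periods, the 95% half-width of the rate difference is 1.96·√(0.03/(60w) + 0.03/240) for a run-in of w weeks:
- w = 2: 1.96·√0.000375 = 0.038
- w = 3: 1.96·√0.000292 = 0.033
- w = 4: 1.96·√0.000250 = 0.031

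The half-width is 0.031/0.03 = 103% to 0.038/0.03 = 127% of the assumed background.

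On the patient scale, if 5% report only in the run-in and 15% only on treatment, the difference is 10 points with half-width 1.96·√((0.20 − 0.10²)/60) = 11 points. With 10% and 30%, it is 20 points with half-width 1.96·√((0.40 − 0.20²)/60) = 15 points.

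**4. Why rates per patient-week.** The periods differ in length. At a constant hazard, a four-week risk of 20% becomes 1 − √0.80 = 10.6% over two weeks, so raw percentages would show a difference where there is none.

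**The case against.** The case on the other side has real weight.

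- **Reporting is not confined to treatment.** A reader of the first sentence of 4.4 might infer that nothing is collected outside the treatment weeks. The documents do not support that. The next sentence invites late-onset reports, 10.1 collects unexpected and serious events from consent, and 9.3.1 is silent on event entry rather than excluding it. This stands.
- **Off-treatment references exist for the gut.** A reader might also infer that background cannot be separated at all. That is too strong. Dyspeptic symptoms are recorded daily in both periods, other gastrointestinal questionnaires are scheduled at all three visits, and causality is assessed. This stands for gastrointestinal complaints. Rash has no evident pre-treatment measure. Headache is unsettled, because the items of the somatization questionnaire taken at entry are not shown. The causality assessment is an open-label judgement and does not supply a rate.
- **The objective is perceived tolerability.** Section 4.4 says so, and perceived side effects arise only once the drug is taken. That justifies keeping an attributed list. It does not reconcile that list with 9.2.4.1 and 10.1.1, or give the tolerability aim in 4.1 a background to be read against.
- **The remedy is weak.** The interval is as wide as the assumed background, so only a large excess would show. Patients know when they are treated, and section 3.5 notes that they tend to present in bad periods, which could raise run-in complaints. This stands and must be stated with the result.
- **Tables belong in an analysis plan.** This is fair for layout. It does not apply to collection: events not asked about in the run-in cannot be recovered by a later analysis plan.

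**Conclusion.** The point holds as a modest but worthwhile correction. Routine participant reporting of non-serious events is described only from the start of treatment and as perceived effects of Amara, while other sections describe events of any cause and a window from consent. As a result, non-serious, non-gastrointestinal complaints have no off-drug rate, and the percentage in 11.4.5 cannot be reliably distinguished from background for them.

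The size, about 5 to 11 of 60 patients on an inert product, rests on an assumed 0.02 to 0.05 events per patient-week and full reporting. It is smaller if patients attribute only some complaints to the drug. The inconsistency between sections does not depend on these assumptions. Nothing here affects the primary outcome, and nothing suggests that serious events would be missed.

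**What to change.** 1. Reconcile sections 4.4, 6.1, 9.2.4.1, 9.3.1, 9.3.2 and 10.1 to one event definition and one window starting at consent.
2. From visit 1, ask the same neutral question in the app or on the paper form: any new complaint, with no mention of Amara.
3. In 11.4.5, report descriptively the number of patients with events and the events per patient-week for run-in and treatment side by side, with the within-patient difference and its 95% CI.
4. Keep events attributed to Amara in a separate table, which preserves the perceived-tolerability objective.
5. State the limits with the result: a wide interval, open-label expectation, reporting fatigue over successive weeks, and presentation during severe periods.

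The cost is a few more entries per patient, one more table, and whatever change the app needs; its configuration is not shown. The synopsis plans first enrolment for July 2022 and this version is dated 10.11.2023. If some patients have already passed the run-in, the comparison is limited to those who enter after the change, and the intervals will be wider than those calculated for 60.
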